reduction of downstream C5 that mediates intravascular hemolysis. Encouraging signs of activity were also observed with APL-2 monotherapy in 3 treatment-naïve PNH patients in the New Zealand phase 1b study APL-2-CP-PNH-204; however, variability in observed responses in this small population suggests additional dose-ranging higher than 270 mg, may be warranted.

- The proposed APL2-CP-AIHA-208 monotherapy trial in AIHA patients targets only C3.
  Given the incomplete understanding of APL-2 monotherapy dose-response in PNH
  patients as described above, the inclusion of two doses of APL-2, 270 mg/day and 360
  mg/day, in the proposed AIHA study will support identification an optimal dose for this
  new disease indication as a C3 complement inhibition monotherapy.
- The proposed 360 mg/day dose is estimated to reach approximately 73% of the Cmax of the NOAEL observed in monkeys after 273 days SC dosing. In addition, Apellis has completed two clinical studies investigating the safety, tolerability, and PK of single APL-CP-0713-1 subcutaneous doses (including 360 mg, and a maximum dose of 1440 mg), and single APL2-CP-HV-401 intravenous doses (up to 2300 mg) of APL-2 in healthy volunteers. Maximum doses from both of these studies appeared to be safe and well tolerated and are estimated to reach approximately 23% and 65% respectively of the Cmax of the NOAEL observed in monkeys. Further support of safety and tolerability comes from emerging data from 2 patients receiving APL-2 360 mg/day for up to 2 months in the ongoing PNH Phase 1b trials.

The self-administration pump can be programmed to deliver in volumes of one mL increments, and no fractions of thereof. As a result, when delivering a dose of 270 mg, a nominal dose of up to 280 mg may be delivered dependent upon the concentration of the formulation (e.g. formulation 40 mg/mL administered in 7mL provides a dose of 280 mg). This difference of approximately 4% is considered an acceptable margin which will have minimal/no impact on the PK/PD or efficacy of APL-2.

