# 5.3.2 Functional Assessment of Chronic Illness Therapy (FACIT) Fatigue Scale

The FACIT Fatigue Scale (Version 4) is an exploratory efficacy endpoint. The individual fatigue score will be calculated as 0-52 (see Section 17.1 of the protocol), where a higher score corresponds to a higher quality of life.

Individual fatigue scores will be listed along with changes from baseline for the ITT Set at each scheduled visit. Study Day 1 will be considered the baseline for the FACIT assessment. If this is missing, change from baseline will not be calculated.

The fatigue score, changes from baseline, and percent changes from baseline will be summarized, using descriptive statistics (mean, SD, median, minimum, and maximum), by randomized dose group and by cohort at each scheduled study visit for both Part A and Part B of the study.

All individual fatigue scores will be plotted by actual study day, where each subject will be identifiable. The mean score  $\pm$  SE for each scheduled visit by dose group and cohort will also be plotted. Individual scores and mean changes from baseline  $\pm$  SE will also be plotted similarly.

The FACIT and all related works are owned and copyrighted by, and the intellectual property of **PPD** Ph.D. Permission for use of the FACIT-FATIGUE questionnaire is obtained by contacting **PPD** at [contact].

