#### 3.3 Study Design

This is a Phase II, open-label, prospective pilot study of APL-2 conducted in subjects with a primary diagnosis of wAIHA or CAD in parallel. The study will consist of up to 24 subjects, a target of 12 subjects with a primary diagnosis of wAIHA in Cohort 1 and a target of 12 subjects with a primary diagnosis of CAD in Cohort 2. Subjects will be randomized 1:1 to a 270mg or 360mg daily SC APL-2 dosage group within each cohort for up to 12 months (Part A, the Core Study Phase).

Following Day 336 and the completion of the Part A Core Study Phase, subjects will be eligible to participate in Part B, a Long-Term Extension Phase, in order to continue to receive treatment with APL-2. The Long-Term Extension Phase is described later in this section.

Through Part A (Day 336), dose escalation from 270 mg/d to 360 mg/d, or deescalation from 360 mg/day to 270 mg/day may occur after a thorough evaluation of available safety and laboratory assessment.

Safety will be assessed throughout the study; serial blood and urine samples will be collected for these assessments. Blood samples will be collected for the assessment of APL-2 PK. Additional samples for assessment of PD will also be collected.

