#### Part B: Long-Term Extension Phase:

Following Visit 15 (Week 48), subjects who elect to continue in the Part B Long-Term Extension Phase will return to the site at 12-week intervals indefinitely until the subject discontinues or the development program is terminated.

Specific procedures for each visit are listed in the Study Flow Chart for the Long-Term Extension Phase in Table 2 in Section 3.3.2.

At Visit 15 (Week 48), subjects electing to enter the Part B Long-Term Extension Phase will begin an APL-2 dose regimen of APL-2 1,080 mg twice weekly (with potential to escalate to APL-2 1,080 mg every 3 days). When switching from the Part A Core Study Phase formulation and dose of APL-2 (270 mg/d or 360 mg/d) to the formulation and dose intended for use in the Long-Term Extension Phase (APL-2 1,080 mg twice weekly), subjects should return to the site for APL-2 administration training and to conduct Dose Transition Visits 1, 2 and 4 weeks after the new dose is initiated and perform the procedures outlined in Appendix Section 8.1.

Subjects who plan on continuing in the Part B Long-Term Extension Phase should be instructed to skip their daily Part A Core Study Phase Dose the day prior to Visit 15 (i.e., the subject should not self-administer APL-2 on Day 335).

**Note:** The first dose of APL-2 1,080 mg should be administered at the Visit 15 (Day 336), with Dose Transition Visits at Week 49, Week 50, and Week 52. Some subjects may enter the Part B Long-Term Extension Phase prior to the availability of the sorbitol formulation. These subjects should continue on their Part A Core Study Phase dose into the Part B Long-Term Extension Phase. These subjects will transition to the Long-Term Extension Phase dose at the next scheduled visit at which the sorbitol formulation and dose is available, and should schedule Visits T1, T2, and T3 1, 2 and 4 weeks following the visit at which the sorbitol dose is initiated. These subjects should be instructed to skip their Part A dose the day before the visit at which the APL-2 1,080 mg twice weekly dose regimen is scheduled to be initiated.

Subjects who discontinue treatment early should complete one Early Termination Follow-up Visit (ETFU) 6 weeks after discontinuation of treatment, and one Early Termination (ET) Exit Visit 6 weeks after the ETFU as outlined in Appendix 8.1.

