# 5. STATISTICAL ANALYSIS METHODOLOGY

In general, tables will be presented by cohort (Cohort 1 wAIHA / Cohort 2 CAD) and study part (Part A + B / Part B). The Part B summaries will start from Study Day 1 in Part B through the end of the Part B Long Term Extension Phase, while Part A + B will start from Study Day 1 in Part A through the end of the Part B Long Term Extension Phase.

Tabulations for continuous data will use a standard set of descriptive statistics for the results and for change from baseline, as specified: number of observations available (n), mean, standard deviation (SD), median, and range (minimum, maximum). Change from Baseline for Part A + B summaries will calculate the Change from Part A Baseline summary statistics. Change from Baseline for Part B summaries will calculate the Change from Part B Baseline summary statistics.

Categorical or dichotomous data will be tabulated using frequencies (counts and percentages). The numerator and denominator for each percentage calculation will be specified in the footnotes of table shells. Categorical data will be populated as appropriate for each study part (Part A + B and Part B).

Data listings will present all information recorded in eCRFs for all subjects and visits. All listings will be sorted by cohort and subject number.

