## • Part B Lab Results:

- Lab results at Part B Baseline and all scheduled Part B visits
- Change from Part B Baseline lab result at all post-baseline visits
- Percent Change from Part B Baseline lab result at all postbaseline visits

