# 5.4.1 Pharmacokinetic Concentration Summaries

APL-2 concentrations reported as below the limit of quantification (BLQ) will be taken as zero for linear plots, and equal to the lower limit of quantification (LLOQ) for semi-logarithmic plots. For the computation of descriptive statistics, BLQ will be taken as zero, except for the calculation of the geometric mean where the LLOQ will be used.

Version 1.0

A listing of all APL-2 concentrations will be presented by dose. The actual study time will be listed, along with the deviation and percent deviation from nominal time.

For Part A, APL-2 concentrations will be summarized by planned study visit windows using descriptive statistics by randomized dose group, actual dose at the time of the visit. That is, at each visit, the descriptive statistics will be presented for:

- All randomized 270mg dose group, regardless of current dose
- All randomized 360mg dose group, regardless of current dose
- Subjects randomized to 270mg and on 270mg dose at time of visit
- Subjects randomized to 360mg and on 360mg dose at time of visit

For Part B, APL-2 concentrations will be summarized by planned study visit windows using descriptive statistics by cohort. The number of subjects with a value > BLQ will also be tabulated.

If a subject discontinues APL-2 dosing, then concentrations from samples collected more than 1 day after the last dose will be excluded from calculations.

For Part A, Linear and log-linear ( $\pm$  SE) concentration profile plots against time will be produced for each dose group.

For Part B, Linear and log-linear ( $\pm$  SE) concentration profile plots against time will be produced for each cohort.

For all time on-study, individual plots will be presented for PK concentration by study day. The individual plots will include an overlay of APL-2 dosing, also aligned by study day.

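### The Part B SAP summarises change from Part B baseline by cohort only, mixing subjects whose nominal weekly dose rises at the switch to 1080 mg with subjects whose dose falls, so a pooled mean can mask changes that differ by prior dose

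*SAP*

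**What the plan says.** Design. Part B SAP section 3.3: "Subjects will be randomized 1:1 to a 270mg or 360mg daily SC APL-2 dosage group within each cohort". Dose changes between the two levels are allowed during Part A. A subject entering Part B "will begin an APL-2 dose regimen of APL-2 1,080 mg twice weekly (with potential to escalate to APL-2 1,080 mg every 3 days").

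Analysis set and baseline. Under Part B SAP section 4.1, the Safety, ITT and PD sets contain only rollovers who took at least one 1080 mg dose. Under section 4.2.2, Part B baseline is the last value before that first dose.

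Layout. Section 5 gives the general rule: "tables will be presented by cohort (Cohort 1 wAIHA / Cohort 2 CAD) and study part". FACIT (5.3.2.3), LASA (5.3.3.3), efficacy laboratories (5.3.4.3) and PD (5.3.5.3) all follow it; the laboratory entry reads "Change from Part B Baseline lab result at all post-baseline visits". For PK, section 5.4.1 says: "For Part B, APL-2 concentrations will be summarized by planned study visit windows using descriptive statistics by cohort". The efficacy and PD figures described in the text are cohort means with SE.

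Other plans for the same data:
- The protocol synopsis (statistical methods) has efficacy changes summarised by cohort and dose group. Protocol 15.2.3 and 15.2.5 ask for efficacy plots and individual PD profiles in which the dose group can be recognised.
- The 2020 SAP, section 5, tabulates by randomised dose within cohort. Its FACIT section extends this to Part B: "by randomized dose group and by cohort at each scheduled study visit for both Part A and Part B of the study". Its LASA and transfusion sections do the same, and its sections 5.3.2 to 5.3.5 plan individual plots.

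**The concern.** Part B baseline is taken on one of two daily doses, and follow-up is on a common regimen. Change from Part B baseline therefore does not measure the same step for everyone in a cohort. If response follows dose, subjects coming from 360 mg/d might lose some control while those coming from 270 mg/d gain. A cohort mean near zero could then mean that the switch made no difference, or that the two groups moved apart.

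The tables as laid out do not separate these readings, although the data to do so are collected and two other planning documents organise the results by dose group.

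**Working it through.** **Inputs.** Part A doses are 270 or 360 mg/d. Protocol 7.2.1 adds that "when delivering a dose of 270 mg, a nominal dose of up to 280 mg may be delivered", and Part B SAP section 2 labels the arm 270/280 mg. The Part B regimen is 1080 mg twice weekly, with possible escalation to every 3 days. The documents state no weekly-dose comparison, so there is no plan figure to reproduce.

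**Weekly dose.** Part A: daily dose × 7. Part B: 1080 × 2 = 2160 mg, or 1080 × 7/3 = 2520 mg on every-3-days dosing.

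| Pre-switch dose | mg/week | Change on twice weekly | Change on every 3 days |
|---|---|---|---|
| 270 mg/d | 1890 | 2160/1890 − 1 = +14.3% | 2520/1890 − 1 = +33.3% |
| 280 mg/d | 1960 | 2160/1960 − 1 = +10.2% | 2520/1960 − 1 = +28.6% |
| 360 mg/d | 2520 | 2160/2520 − 1 = −14.3% | 2520/2520 − 1 = 0% |

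In a cohort split equally at nominal doses, mean weekly dose goes from (1890 + 2520)/2 = 2205 mg to 2160 mg, a fall of 45 mg (2.0%). The cohort average hardly moves while its two halves move by about 14% each way.

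**How much a pooled mean can hide.** Pooled mean = (n270 × e1 + n360 × e2)/(n270 + n360). Assume, for illustration only, changes of +1 and −1 unit:
- 6:6 or 5:5 split: 0
- 4:5 split: (4 − 5)/9 = −0.11
- 3:6 split: (3 − 6)/9 = −0.33
- 5:2 split: (5 − 2)/7 = +0.43

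Masking is complete only with equal numbers and equal, opposite changes. With unequal numbers it is partial.

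**Possible size of the changes.** Assume an Emax curve in weekly dose, E = D/(D + ED50), with ED50 between 945 and 3780 mg/week. The documents give no such curve. The move from 1890 to 2160 mg then gains 0.029 to 0.033 of the maximum effect, and the move from 2520 to 2160 mg loses 0.032 to 0.038. The equal-weight mean lies between −0.001 and −0.003. On such curves the masking is nearly complete with equal arms, but the effects are themselves small.

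**Whether the reported SD would reveal it.** With equal arms, within-arm SD of 1 and changes of ±e, pooled SD is about √(1 + e²): 1.12 for e = 0.5 and 1.41 for e = 1. A moderate divergence widens the SD only slightly, and the SD does not show which group moved.

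**The case against.** Several points on the other side stand.

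- **Cancellation is not shown.** A reader might infer that opposite effects cancel in every change-from-Part-B-baseline table. The documents do not support that: they give no evidence of a response to a dose change of about 14%, no rollover numbers by arm, and allow every-3-days dosing, where the contrast becomes +33% against 0%.
- **The switch is not a clean dose contrast.** Formulation goes from mannitol to sorbitol and schedule from daily to twice weekly at the same time. Reading weekly dose as exposure assumes linear PK and equal bioavailability. The protocol's Part B dose rationale (17.3.3) was not in the text available for this check.
- **The dose-finding aim belongs to Part A.** Protocol 7.2.1 says that two doses "in the proposed AIHA study will support identification an optimal dose for this" new indication. That concerns 270 against 360 mg/d, which the 2020 SAP addresses by randomised dose. It does not promise a dose comparison in Part B.
- **Other outputs help.** Median and range accompany each mean and SD. Efficacy and PD results are listed by subject with change from Part B baseline, and individual PK plots carry a dosing overlay. With at most 12 planned subjects per cohort, a reader could trace individuals.
- **The Part B SAP may differ.** It is descriptive, supersedes the protocol's statistical section, and sets its layout as a general rule. Its list of planned outputs (Appendix 8.2) was not available, so the absence of dose-split displays is read from the body text.

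One might also infer that dose group was dropped because of the statement on subgroups (Part B SAP 4.5). The SAP does not say so, and the 2020 SAP carries the same sentence while tabulating by dose.

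What remains is that listings and spread do not replace a summary by prior dose, and no specific reason is given for removing one.

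**Conclusion.** The point holds as a limitation of presentation. Tables of change from Part B baseline combine nominal weekly dose changes of +14.3% (+10.2% from 280 mg/d) and −14.3% in one column per cohort, so a mean near zero cannot be read as no effect of the switch. The dose figures rest on nominal doses and twice-weekly administration. How much is masked depends on a dose response and a rollover split that the documents do not give, so it may be anything from nothing to nearly all of a divergence between the groups.

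The departure from the protocol and from the 2020 SAP is documented. It is permitted by the precedence clause, but not explained. Because formulation and schedule change too, even a split display would describe what followed the switch by prior dose; it would not isolate the effect of dose. The change is worth making because it is cheap and restores a layout already planned.

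**What to change.** In Part B SAP section 5, with matching edits in 5.3 and 5.4:

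- Add to the Part B efficacy, PD and PK tables and mean figures descriptive columns within cohort by the daily dose taken immediately before the first 1080 mg dose (270/280 against 360 mg/d). Keep the cohort total.
- Show both randomised dose and pre-switch dose in the listings.
- Restore individual haemoglobin and C3 profiles across the switch, identified by pre-switch dose, and mark any later move to the more frequent regimen.
- If dose group is still left out, state why.

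When making the edit, reconcile the regimen wording. Part B SAP sections 2 and 5.1.6.1 speak of three times weekly (3 × 1080 = 3240 mg/week), while section 3.3 and the compliance formula speak of every 3 days (2520 mg/week).

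Cost: two more columns per table and some figures, from data already held, with no new inference. The downside is small cells, at most about 6 per arm and cohort if nobody changed dose and fewer after dropout. Where dose changed in Part A, the grouping may differ from the randomised arm, so the results are descriptive only.

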### 5.1 Study Subjects

### 5.1.1 Subject Disposition

The subject disposition will summarize All Enrolled Subjects from Screening prior to Part A through the end of Part B. The following disposition categories will be tabulated by cohort (Cohort 1 wAIHA / Cohort 2 CAD):

- o Number of subjects screened
- Screen Failure Reasons
- Number of subjects who discontinued prior to the first dose of APL-2

Apellis Pharmaceuticals, Inc. Protocol: APL2-CP-AIHA-208 Part B Long Term Extension Statistical	Analysis Plan	Version 1.0	08 Nov 2022
0	Number of sub	jects who receive	e at least at least one dose of
	APL-2 in Part	A phase (Safety	V Set in Part A Core Study
	Phase)		
0	Number of sub	jects who comple	eted treatment phase through
	Visit 15		
0	Number of sub	jects in the Part A	A PP Set
0	Number of ear	ly termination s	ubjects during Part A Core
	Study Phase wi	th reason for ear	ly termination
0	Number of s	subjects who d	liscontinued after Part A
	completion and	l prior to Part B v	with reason for termination
0	Number of sub	jects who receive	e at least one 1080 mg APL-
	2 dose in Part H	B phase (Safety/I	TT/PD Set)
0	Number of sul	bjects in Per Pr	otocol set per definition in
	Section 4.2		
0	Number of sub	jects in PK set	
0	Reason for Wit	hdrawal during I	Part B Long Term Extension
	Phase		

# 5.1.2 Protocol Deviations

A protocol deviation is any change, divergence, or departure from the study design or procedure defined in the protocol.

The following categories will be used to group protocol deviations:

- 1. Eligibility Not Met
- 2. Study Assessment Noncompliance
- 3. Study Drug Noncompliance
- 4. Study Schedule Noncompliance
- 5. Other

The following are categorical reasons used to document why a protocol deviation occurred:

- 1. Subject Illness
- 2. Subject Unable to Comply

3.	Subject Refusal
4.	Clinical/Site Error
5.	Laboratory Error
6.	Investigator/Staff decision

7. Other

Subsets of the protocol deviations can be identified as major and minor protocol deviation as described below:

Major Protocol Deviation: A protocol deviation that might significantly affect the completeness, accuracy, and/or reliability of the study data or that might significantly affect a subject's rights, safety, or well-being.

Minor Protocol Deviation: A protocol deviation that will not significantly affect the completeness, accuracy, and/or reliability of the study data and that will not significantly affect a subject's rights, safety, or well-being.

Upon soft lock of database, all documented protocol deviations in the study will be reviewed to identify all major and minor protocol deviations by a data review team including representatives from DPC clinical operations, medical, data management, and statistics, and sent to the sponsor for approval. Final decisions will be documented in the eTMF and incorporated into the CDISC datasets (SDTM DV and ADaM ADDV).

All protocol deviations will be listed. A separate listing will include only the major protocol deviations.

The following protocol deviation summaries will be tabulated by cohort (Cohort 1 wAIHA / Cohort 2 CAD) for Part A + B and Part B. The study part will be determined by the protocol deviation start date, i.e. protocol deviations that began at any point during Part A or Part B will be

summarized in Part A + B and protocol deviations that began on or after the date of first 1080 mg APL-2 dose (Part B Study Day 1) will be summarized in Part B.

Version 1.0

## • Part A + B:

- The number of deviations and number/proportion of subjects with protocol deviations during Part A + B and with major protocol deviations during Part A + B.
- The number of deviations and number/proportion of subjects with each protocol deviation category during Part A + B.

## • Part B:

- The number of deviations and number/proportion of subjects with protocol deviations during Part B and with major protocol deviations during Part B.
- The number of deviations and number/proportion of subjects with each protocol deviation category during Part B.

### 5.1.3 Demographics and Baseline Characteristics

The following demographics will be tabulated by cohort (Cohort 1 wAIHA / Cohort 2 CAD) using summary statistics for continuous parameters and frequency/percent for categorical parameters at Part A Core Study Phase Baseline for Safety/PP Analysis Set:

- Age
- Sex
- Race
- Ethnicity
- Baseline Height
- Baseline Weight
- Baseline BMI

The following baseline characteristics will be tabulated using summary statistics for continuous parameters and frequency/percent for categorical parameters as well:

Version 1.0

- Time since diagnosis of wAIHA or CAD
- CH50
- AH50
- Complement C3
- C3d Type I, Type II, Type III
- Reticulocytes
- Haptoglobin
- Hemoglobin
- Anaemia categories (Mild: Hemoglobin ≥ 10 / Moderate: 5 ≤ Hemoglobin < 10 / Severe: Hemoglobin < 8)

- Plasma Hemoglobin
- Direct Antiglobulin Test (Negative / Positive)
- Baseline Cold Agglutinins (< 1:32 / 1:128 / 1:256 / 1:512 / > 1:512)
- Anti-C3 Coombs (Negative / WKPOS / 1+POS / 2+POS / 3+POS / 4+POS)
- Number of Transfusions Per Month in 12 Months Prior to First Dose (derived as the number of Packed Red Blood Cell transfusions in the 365 days prior to first APL-2 dose\*365/28)

